4.1.19. Handling of Incomplete or Missing Dates Associated with an Event

An incomplete date occurs when the exact date an event (e.g. an adverse event) occurred or ended cannot be obtained from a subject. The database contains data fields for month, day, and year. A date is incomplete if at least one of these three fields is not known.

For many of the planned analyses, a complete date is necessary to determine if the event should be included in the analysis (e.g. if the event is treatment-emergent) or to establish the duration of an event. In such cases, incomplete dates will be imputed as described below.

For the purposes of handling partially reported start and stop dates for an event the following algorithm will be applied:

- Missing start day, but month and year present:

If the event occurs same month and year as the occurrence of IMP, then the start day of the event will be assigned to the day of first dose of IMP (i.e., Day 1).

Otherwise the start day will be set to the first day of the month.
- Missing start day and month, but year present:

If event occurs in the same year as IMP, then the start date of the event will be assigned to Day 1.

Otherwise the start day and month will be set to 01 January.

- In the unlikely event of a completely missing start date (year not present), the start date will be imputed as Day 1.
- Missing end day, but month and year present:
The day will be set to the last day of the month.
- Missing end day and month, but year present:
The end day and month will be set to the date of study completion. However, if study completion year is greater than the year of the event, then the day and month will be set to 31 December.
- Missing all components of an end date and the event is not marked as ongoing:
The event will be considered as ‘ongoing’ and will be considered treatment-emergent if the start date is on or after Day 1.

If any imputed start date causes the start date to occur after the end date, the end date will be used for the imputation of the start date. If any imputed end date causes the end date to occur prior to the start date of the event, the start date of the event will be used for the imputation of the end date. If the imputed date is later than the date of study withdrawal, then the date of study withdrawal will be used to impute the date in question. In subject data listings, start and stop date of events will be displayed as reported on the eCRF (i.e., imputed values will not be listed).

4.1.20. Handling of Alphanumeric Data

Should there be instances where a clinical laboratory parameter is reported with imbedded non-numeric characters, as for example, “<0.1” or “>10”, the data will be imputed as described below for quantitative summaries. The actual alphanumeric values as reported in the database will be presented in data listings.

- The values < LLN will be replaced with ½ the value of the lower limit. For example, “< 0.1” will be replaced with 0.05 if the LLN is 0.1.
- The values > ULN will be replaced by values of increased precision by one level. For example, “>0.1” will be imputed to “0.11” if the ULN is 0.1, and “>10” will be imputed to “10.1” if the ULN is 10.

Additionally, in the event of the upper limit of normal (ULN)/lower limit of normal (LLN) reported as alphanumeric (e.g., ‘<5’, ‘≤5’, ‘>5’, ‘≥5’), the determination of the laboratory toxicity grade or out-of-range status will be based on the convention on the ULN and LLN below:

- If the ULN is in the form of ≤5, only the numeric part will be used for determining the toxicity grade of the test results (i.e., the ULN is set to 5). If the ULN is in the form of <5, the numeric value of the ULN will be decreased by two levels of precision in the direction of the symbol (i.e., the ULN is set to 4.99).
- If the LLN is in the form of ≥5, only the numeric part will be used for determining the toxicity grade of the test results (i.e., the LLN is set to 5). If the LLN is in the form of

>5, the numeric value of LLN will be increased by two levels of precision in the direction of the symbol (i.e., the LLN is set to 5.01).

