5.15.5. Clinical Laboratory Assessments

Descriptive summaries of selected (quantitative) clinical laboratory results will be presented by treatment group and study visit. Laboratory values outside the normal range for each systematically collected hematology, blood chemistry, and urinalysis parameter will be identified. Each subject's hematology, blood chemistry, and quantitative urinalysis values will be flagged as "low" (below the lower limit of normal/LLN), "normal" (within the normal range), or "high" (above the upper limit of normal/ULN) relative to the normal ranges of the central laboratory. Each subject's qualitative urinalysis results will be flagged as "normal" or "abnormal." In addition, toxicity grade will be determined for laboratory tests with toxicity grade based on Common Terminology Criteria for Adverse Events (CTCAE) Version 5.0 with implementation specifications in [Section 9.8](#). The result of each laboratory test for individual

subjects will be presented in a listing with the normal range defined by the central laboratory, the status relative to the normal range, and the CTCAE toxicity grade.

Shift table will be used to summarize shifts from baseline toxicity grades to greatest (worst) treatment-emergent laboratory toxicity grades based on CTCAE criteria. For hematology and, blood chemistry, and quantitative urinalysis parameters that no CTCAE toxicity grade was defined, a shift table for each laboratory test will be based on the shift from baseline high/normal/low status to the status of the maximum post-baseline value and the minimum post-baseline value (including test results from unscheduled visits, if any). Similarly, for qualitative urinalysis parameters, shifts from baseline normal/abnormal status to the worst post-baseline status will be summarized.

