5.16.1. Pharmacokinetic Data Analysis

Plasma concentrations of tavapadon and CV-0000053 (metabolite) will be summarized separately using descriptive statistics by visit. Plasma concentrations of tavapadon and CV-0000053 that are <LLOQ will be reported as 'BLQ' in the data listings. Plasma concentrations that are BLQ will be treated as 0 for calculation of descriptive statistics. The geometric mean, however, will be calculated by imputing BLQ values as $\frac{1}{2}$ LLOQ. If the calculated mean concentration is below the limit of quantitation, the mean will be reported as BLQ and the SD and CV% shall be reported as not determined (ND). Mean plasma concentrations (SD) of tavapadon and CV-0000053 will be also be plotted versus time based on nominal visit.

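### SAP 4.1.20 imputes censored laboratory results from the limits of normal rather than the reported limit; read literally, a `<x` result can become a number above x

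*SAP*

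**What the plan says.** SAP 4.1.20 deals with laboratory results that carry a non-numeric character, such as `<0.1` or `>10`. It states that "the data will be imputed as described below for quantitative summaries", while data listings show the result as reported. Two rules follow.

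- Low results: "The values < LLN will be replaced with ½ the value of the lower limit". The example is that `<0.1` "will be replaced with 0.05 if the LLN is 0.1".
- High results: "The values > ULN will be replaced by values of increased precision by one level". The examples are `>0.1` to 0.11 when the ULN is 0.1, and `>10` to 10.1 when the ULN is 10.

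The next paragraph of the same section gives a separate convention for grading and out-of-range status, to apply "in the event of the upper limit of normal (ULN)/lower limit of normal (LLN) reported as alphanumeric". That fixes the meaning of LLN and ULN as limits of normal. SAP 5.15.5 uses the abbreviation in the same sense when it flags a result as low: "below the lower limit of normal/LLN".

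**The concern.** A result reported as `<x` carries one piece of information: the true value is below x. The number x belongs to the report; the limit of normal belongs to the reference range. The two need not coincide. A rule that takes half the limit of normal can therefore return a number that the report itself rules out.

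The trigger raises a second question. Both bullets apply only to values outside the normal range, so a censored result that is not known to be outside it has no stated treatment.

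At stake are the laboratory summaries by treatment group and visit in SAP 5.15.5. Under SAP 5.1 these include the mean, standard deviation, quartiles, minimum and maximum. SAP 9.5 calls for results to be verified by independent programming. Two programmers could resolve this wording differently, and the one who follows it literally would produce the wrong number.

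**Working it through.** **Inputs.** The two rules, the three worked examples and the meaning of LLN/ULN are all from SAP 4.1.20. The documents give no normal ranges or reporting limits, so every LLN and ULN below, other than those in the SAP's examples, is an assumption for illustration.

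**Rule as written.** A `<x` result is known to be below the LLN when x ≤ LLN, and it then becomes LLN/2. A `>x` result is known to be above the ULN when x ≥ ULN. If the added precision is applied to the ULN, it then becomes the ULN plus one unit at the next decimal place. Otherwise no rule applies.

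**Comparison rule, from the reported number.** `<x` becomes x/2; `>x` becomes x plus one unit at the next decimal place.

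**Step 1: the SAP's own examples.**

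- `<0.1`, LLN 0.1: rule as written 0.1/2 = 0.05; comparison rule 0.1/2 = 0.05.
- `>0.1`, ULN 0.1: both give 0.1 + 0.01 = 0.11.
- `>10`, ULN 10: both give 10 + 0.1 = 10.1.

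Both rules reproduce all three figures, because every example sets the limit of normal equal to the reported number. The examples cannot distinguish the rules.

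**Step 2: let the LLN differ from x, with the result held at `<0.1`.**

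| Assumed LLN | Rule as written (LLN/2) | From reported number (x/2) | Consistent with `<0.1`? |
|---|---|---|---|
| 0.1 | 0.05 | 0.05 | yes |
| 0.15 | 0.075 | 0.05 | yes |
| 0.2 | 0.10 | 0.05 | no (equals 0.1) |
| 0.3 | 0.15 | 0.05 | no |
| 0.5 | 0.25 | 0.05 | no |
| 1.0 | 0.50 | 0.05 | no |
| 0 or 0.05 | no rule | 0.05 | – |

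The imputed value exceeds x exactly when LLN/2 > x, that is, when x < LLN/2. In that case it is too high by at least LLN/2 − x, whatever the true value is. With x = 0.1 and LLN = 0.5 that is 0.25 − 0.1 = 0.15. This bound does not depend on accepting x/2 as the right substitute.

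**Step 3: high results, with the result held at `>10`.** If precision is added to the ULN, an assumed ULN of 8 gives 8.1 and an assumed ULN of 5 gives 5.1, both below 10 and so contradicting the report. If precision is added to the reported number, the value is 10.1 in both cases and there is no contradiction. The bullet does not say which is meant.

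**Step 4: results not known to be outside the range.** `<0.1` with an LLN of 0 or 0.05, and `>10` with a ULN of 12, meet neither bullet. This gap exists under either reading of the high rule.

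**The case against.** The strongest reply is that the authors meant the reported limit. The section opens with reported values such as `<0.1`, the low bullet halves the lower limit without repeating LLN at that point, and all three examples fit the reported-number rule. On that view this is loose wording, not a wrong method. Much of that stands: the intent may well have been the reported limit. But the trigger is the LLN, the section spells LLN out as a limit of normal, and the low example is made conditional on the value of the LLN. A programmer following the text would halve the limit of normal. Even on the charitable reading, the trigger still leaves censored in-range results without a rule.

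Several stronger readings are tempting and are not supported.

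- A reader might infer that in-range censored results are dropped and that means are biased as a result. The SAP states no treatment for them; exclusion is one possible outcome, not a stated one.
- A reader might infer that marked decreases are hidden. For a positive LLN, LLN/2 is still below the LLN, so the result would still be flagged low. SAP 5.15.5 also plans shift tables, and the listings show the reported value.
- A reader might infer that laboratory changes from baseline are affected. SAP 5.15.5 does not list change-from-baseline summaries for laboratory data, unlike the vital-sign and ECG sections.
- A reader might point to SAP 5.16.1 as the model to follow, since "The geometric mean, however, will be calculated by imputing BLQ values as" half the LLOQ. That applies to the geometric mean only; for the other descriptive statistics the same section sets such values to 0.
- A reader might name particular tests as affected. Protocol Appendix 2 lists the tests, but nothing says which of them will be reported as censored.

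**Conclusion.** The point holds as a minor defect in a stated rule. Read literally, SAP 4.1.20 gives a `<x` result a value above x whenever x < LLN/2. For high results the base number is not named, and only the reading that uses the ULN can contradict the report. Censored results not known to be outside the normal range have no rule.

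The reach is small: descriptive laboratory statistics such as the mean and minimum. SAP 5.1 reserves statistical testing for the efficacy endpoints, and no efficacy result uses these numbers. The SAP does not say whether toxicity grading uses the imputed number, so no claim is made there.

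The size cannot be stated, because the documents give no reference ranges, reporting limits or frequency of censored results. The value of 0.25 for `<0.1` rests on an assumed LLN of 0.5 and shows only how the rule behaves.

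**What to change.** Replace the two imputation bullets in SAP 4.1.20 with: *A result reported as <x is set to x/2, and a result reported as >x is set to x increased by one unit at the next decimal place, where x is the number in the reported result, whether or not x equals the LLN or ULN.* Leave the separate ULN/LLN convention for grading and out-of-range status unchanged.

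This keeps the SAP's three example values (0.05, 0.11 and 10.1), always respects the reported inequality, names the base number for high results, and covers in-range results. The cost is two lines of text. The programming becomes simpler, since the imputation no longer needs the normal range.

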4.2. Visit Windows

Data collected longitudinally across visits will be summarized and analyzed by visit.

Laboratory data will be presented according to the nominal visit as collected from the eCRF or laboratory data unless the visit is an early termination or unscheduled visit. Early termination and unscheduled visits will be assigned visit windows based on the study day completed according to [Table 3](#). Other assessment data, including efficacy assessments and Hauser diary data, will be mapped to the appropriate time point based on the window as defined in [Table 3](#) from Baseline to Week 22 to appropriately captured time of assessment in cases of visit schedule variations. Due to the short interval between Visit 10 (Week 26) and Visit 11 (Week 27), data obtained at the nominal visit at these two time points will be used for completed subjects. Early termination and unscheduled visits will also be mapped to visit based on the study day completed according to [Table 3](#).

Table 3: Visit Windows

Analysis Visit	Analysis Visit Target Day	Analysis Visit Window
Baseline	1	≤ 1
Day 1*	1	1
Week 2	14	2 - 24
Week 5	35	25 - 45
Week 8	56	46 - 66
Week 11	77	67 - 86
Week 14	98	87 - 111
Week 18	126	112 - 140
Week 22	154	141 - 168
Week 26	182	169 - 185
Week 27	189	186 and higher

* Day 1 assessments are pre-IMP except ECG with a 60 minute post-dose assessment

If assessments are collected multiple times within a given visit window the result closest to the analysis visit target day will be used for summary presentations. If two measurements have the same distance to the target day, the later value will be used. If a subject has multiple non-missing values on the same date, then the last one is used, as determined by the time collected, if available.

5. STATISTICAL ANALYSIS METHODS

5.1. General Considerations

Descriptive statistical methods will be used to summarize the data from this trial, with statistical testing performed for the efficacy endpoints. Unless stated otherwise, the term “descriptive statistics” refers to number of subjects (N), number of observations (n), arithmetic mean, median, standard deviation (SD), geometric mean and coefficient of variation (CV%) (for concentration data only), first quartile (Q1), third quartile (Q3), minimum, and maximum for continuous data, and frequencies and percentages for categorical data. Certain figure presentations will include the standard error of the mean (SE). The term “treatment group” refers to treatment assignment: placebo and tavapadon 5-15 mg. All data collected from subjects who sign the informed consent form, including screen failures, will be included in data listings. Unless otherwise noted, the data listings will be sorted first by treatment group and subject number and then by date within each subject number.

The number and proportion of missing visits and key assessments due to COVID-19 control measures and the frequency of remote assessments performed due to COVID-19 restrictions will be tabulated by treatment, visit, and assessment as well as the overall number and proportion of subjects with any such missing visits, assessments, or remote visits in each treatment group.

The statistical analyses will be conducted with the SAS® software package version 9.4 or higher.

5.2. Populations for Analyses

The analysis populations are defined [Table 4](#).

Table 4: Populations for Analysis

Population	Description	Analysis
ITT	All randomized subjects	Demographic and Baseline Characteristics
FAS	All randomized subjects who receive at least 1 dose of IMP. This will be the safety analysis set.	Safety analysis
mITT	All randomized subjects who receive at least 1 dose of IMP and have both a valid baseline and at least 1 postbaseline valid Hauser diary entry	Primary analysis set for efficacy
Endpoint completers	All subjects in the mITT population who complete a valid Hauser diary at endpoint	Sensitivity analysis for efficacy
PK Analysis Set	All randomized subjects who receive at least 1 dose of IMP and have at least 1 measurable tavapadon (CVL-751) concentration	PK analysis

Abbreviations: FAS = full analysis set, IMP = investigational medicinal product, ITT = intent-to-treat, mITT = modified intent-to-treat, PK = pharmacokinetic.

5.3. Statistical Hypotheses

The primary and key secondary hypotheses are summarized below. All will be tested based on 2-sided.

Primary Endpoint	Tavapadon 5-15 mg QD vs Placebo
Change from baseline to Week 26 in total daily “on” time without troublesome dyskinesia based on the 2 day average of the self-completed home diary for motor function status (Hauser diary)	$H_1 : \mu_{\text{active}} = \mu_{\text{placebo}}$ vs $\mu_{\text{active}} \neq \mu_{\text{placebo}}$
Key Secondary Endpoint	
Change from baseline to Week 26 in total daily “off” time based on the 2 day average of the self completed home diary for motor function status (Hauser diary)	$H_2 : \mu_{\text{active}} = \mu_{\text{placebo}}$ vs $\mu_{\text{active}} \neq \mu_{\text{placebo}}$

5.4. Multiplicity Adjustment

A sequential testing approach will be taken to control the overall Type I error rate with respect to the primary and key secondary hypotheses. The primary endpoint of tavapadon will be compared with that of placebo (H_1) at the final analysis at α level of 0.049 to ensure that, with the interim analysis taken into consideration, the overall α for H_1 is <0.05 (Section 9.1). If H_1 is successful, the available α of 0.05 will be passed along fully ($r=1$) to the secondary hypothesis H_2 (α level for H_2 can be 0.05 instead of 0.049 as the key secondary endpoint will not be part of the interim analysis). Other secondary endpoints are considered as supportive in nature and will be tested at the nominal level without further rank ordering.

5.5. Strata and Covariates

No stratification was implemented in randomization. The baseline value of each efficacy variable will be included as a covariate in the efficacy analyses.

5.6. Subject Disposition, Demographic and Baseline Characteristics

Subject disposition will be based on the ITT population with tabulation of the number of subjects who complete the study and the number of discontinued and from the study and the reasons by treatment group. Additionally, the number of days on study will be summarized.

Tabulation of subject randomization by country and site will be presented for the ITT population and for completed subjects. A listing of randomization number, subject, treatment randomized, country, and site will be provided. Further tabulation by region (United States, Non-US) and country will also be presented. Subject disposition data will also be tabulated for all subjects screened to include the number of subjects screened, the number of screen failures, and the reason for screen failure.

Kaplan-Meier (KM) plots will be used to assess time to discontinuation of study, time to discontinuation of study due to adverse events, and time to discontinuation of study due to subject withdrawal. The complete subjects will be censored at the time of end of study for the KM analyses.

Number of subjects in each analysis population set will be summarized.

Demographic data and baseline characteristics including age, age categorical distribution, gender, childbearing potential, race, ethnicity, height at screening, weight at screening and baseline, BMI at screening and baseline, history of Parkinson's disease (including years from initial diagnosis), baseline on time without troublesome dyskinesia, baseline off time, Montreal Cognitive Assessment (MoCA) total score, Modified Hoehn & Yahr assessment at screening, MDS-UPDRS score at baseline, and L-dopa dose at baseline will be summarized using descriptive statistics for the ITT population. Use of PD medications (ATC classifications of ADAMANTANE DERIVATIVES, OTHER DOPAMINERGIC AGENTS, OTHER ANTIPARKINSON DRUGS, MONOAMINE OXIDASE B INHIBITORS, or ANTICHOLINESTERASES) at baseline will also be summarized. Further tabulation by region and country will also be presented.

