7.3 Individual Subject Discontinuation

After treatment assignment, a subject may stop treatment permanently for a variety of reasons. Treatment discontinuation may be initiated by a subject who is not satisfied with

treatment or may become medically necessary due to AEs, required treatment with a disallowed medication or therapy, or other issues, as determined by the investigator.

A subject may discontinue the IMP for any of the following reasons:

- Adverse event
- Death
- Worsening of PD symptoms to such an extent that, in the judgment of the investigator, the subject requires additional anti-PD medications
- Treatment with prohibited concomitant medications
- Noncompliance with study schedule
- Noncompliance with study drug
- Withdrawal by subject
- Pregnancy
- Physician decision

If a subject discontinues the IMP due to an AE, the investigator or other trial personnel will make every effort to follow the event until it has resolved or stabilized.

All subjects have the right to withdraw consent for further participation in the trial at any time without prejudice. Subjects cannot withdraw consent for use of data that have already been collected as part of the trial but can withdraw consent for future participation. The investigator can also discontinue a subject from the trial at any time if medically necessary. Unless the subject provides written withdrawal of consent or there is other written documentation by the investigator confirming the subject's verbal intent to completely withdraw from the trial, subjects should be followed for all protocol-specified evaluations and assessments, if possible.

Complete withdrawal of consent requires a subject to refuse of ALL of the following methods of follow-up:

- Participation in all follow-up procedures specified in the protocol (whether in-clinic or by telephone)
- Participation in a subset of protocol specified follow-up procedures (by a frequency schedule and method, as agreed by subject and staff)
- Contact of the subject by trial personnel, even if only by telephone, to assess current medical condition, and obtain necessary medical or laboratory reports relevant to the trial's objectives
- Contact of an alternative person(s) who has been designated in source records as being available to discuss the subject's medical condition, even if only by telephone, mail, or e-mail (eg, family, spouse, partner, legal representative [as defined per local regulations], friend, neighbor, or physician)

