1.1. Study Overview

This is a prospective, Phase 3, multicenter, multinational, randomized, double blind, placebo controlled, parallel group, 27 week trial to evaluate the efficacy, safety, tolerability, and pharmacokinetics (PK) of flexible doses of tavapadon (5 mg to 15 mg once daily [QD]) as adjunctive therapy to levodopa (L Dopa) in male and female subjects aged 40 to 80 years who have a diagnosis of PD (consistent with the UK Parkinson's Disease Society Brain Bank diagnostic criteria); a modified Hoehn and Yahr score of 2, 2.5, or 3 in the "on" state; a minimum of 2½ hours of "off" time on 2 consecutive days; and a good response to L Dopa in the judgment of the investigator. The trial will include a Screening Period (maximum of 4 weeks), a 27 week Treatment Period, and a 4 week Safety Follow up Period. Details of schedule of assessments are provided in [Section 9.2](#).

A total of 368 subjects are planned to be randomized in a 1:1 ratio to receive tavapadon or placebo once daily (184 subjects per treatment group). The dose of tavapadon will be titrated and adjusted over the first 13 weeks of the trial and then maintained for 14 weeks. The planned duration of treatment is 27 weeks, including the Titration and Maintenance Phases. The investigational medicinal products (IMPs) will be taken orally.

The trial design is depicted in [Figure 1](#).

Figure 1: Trial Schematic

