1.2. Sample Size Considerations

A sample size of 184 subjects per group (total, 368 subjects) will provide at least 90% power to detect a change in the primary outcome measure (change from baseline in "on" time without troublesome dyskinesia) of 1 hour with a standard deviation of 2.5, a 2 sided alpha level = 0.049, and assuming a 27% dropout rate. The sample size calculation was based on a two-sample t-test with equal variance.

Given that the assumptions for the sample size were based on a preliminary study of limited sample size using a different dosing schedule, it is unknown if the assumption of a standard deviation of 2.5 is a reasonable estimate of the population variability and appropriate for this study as designed. To this end, an interim analysis of the primary efficacy endpoint will be included to assess the adequacy of the overall sample size relative to achieving the study objectives. [Section 9.1](#) provides further detail on the conduct of the interim analysis. Should the interim analysis indicate a requirement of sample size increase per pre-defined decision rule ([Section 9.1](#)) to maintain statistical power, Cerevel will extend enrollment to achieve the required sample size.

In the event of higher than anticipated early terminations due to COVID-19 or other reasons, Cerevel may also extend enrollment in order to maintain the planned statistical power.

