9.1.2. Operational Characteristics of the Interim Sample Size Re-estimation

9.1.2.1. Power Loss with Original Sample Size Under Circumstance of Increased Variability

The originally planned sample size depends on the assumption of the standard deviation of 2.5 hours in “daily on time without dyskinesia”. [Table 5](#) below illustrate the impact on the power of the study of a deviation from the assumption when an increased SD is observed in the study population. It is clear that the study may have substantially increased risk of not achieving its primary objective should this happen. Therefore, an interim sample size re-estimation with realistic SD assumption is important for the study.

Table 5: Impact of Standard Deviation Assumption on Statistical Power

Fixed Sample Size of N=368 (270 completers with 27% DC rate)		
	Type I error rate (α)	Power to detect $\Delta \geq 1$ hr vs Placebo
SD = 2.5 hr	0.049	90.4%
SD = 3.0 hr	0.049	77.6%
SD = 4.0 hr	0.049	53.1%

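### SAP 5.6 gives no rule for other-cause exits in its two cause-specific Kaplan-Meier discontinuation curves; the usual default tends to overstate each cause, by about 1 point at the planned dropout

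*SAP*

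**What the plan says.** SAP 5.6 plans three Kaplan-Meier plots. It states that "Kaplan-Meier (KM) plots will be used to assess time to discontinuation of study, time to discontinuation of study due to adverse events", and the list ends with a third plot, for subject withdrawal. The one censoring rule reads: "The complete subjects will be censored at the time of end of study for the KM analyses". Nothing is said about a subject who leaves for a reason other than the one plotted.

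The same section tabulates "the number of discontinued and from the study and the reasons by treatment group", for the ITT population, so the crude proportion for each reason will also be reported.

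The list in Protocol 7.3 opens "A subject may discontinue the IMP for any of the following reasons" and names nine, among them adverse event, death, worsening of PD, prohibited medication, noncompliance, withdrawal by subject and physician decision. That list concerns stopping the IMP. The reasons for discontinuation named in SAP 5.9.3.3 are similarly varied.

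The only dropout figure is the overall one in SAP 1.2, "assuming a 27% dropout rate". It is not split by cause or by arm.

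**The concern.** A subject who leaves for one reason can no longer leave for another, so the reasons compete. The completer rule is enough for the all-cause curve, because every exit is then an event. It is not enough for a single-cause curve.

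With no rule, a programmer would most likely censor other-cause exits on the day they happen. 1-KM then estimates the probability of leaving for that cause in a setting where nobody leaves for any other. It has that meaning only if the other exits are non-informative. SAP 5.9.3.3 treats exits by subject withdrawal and physician decision as missing not at random. That choice concerns the efficacy outcome, but it shows that these exits are not assumed to be ignorable.

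What is at stake is agreement between outputs. Discontinuation for adverse events is a prominent tolerability result for a titrated drug, and the plotted curve should end at the proportion shown in the disposition table.

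**Working it through.** **Inputs from the documents.** Overall dropout D = 27% (SAP 1.2). SAP 9.1.2.1 gives "Fixed Sample Size of N=368 (270 completers with 27% DC rate". Subjects are "randomized in a 1:1 ratio to receive tavapadon or placebo once daily (184 subjects per treatment group" (SAP 1.1). Treatment lasts 27 weeks, or 189 days. Every split by cause, every arm-specific rate and every D other than 27% below is an assumption.

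**The plan's own figure.** The documents give no figure for these curves. The one stated result that uses the dropout rate is the power. 184 × 0.73 = 134.3, rounded up to 135 per arm, or 270 in total. For a difference of 1 h, SD 2.5 and two-sided alpha 0.049, the noncentrality is 1/(2.5 × √(2/135)) = 3.29 on 268 degrees of freedom, which gives 90.4% power. SAP Table 5 states 90.4%, so the figure reproduces.

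**Formulas.** Let f be the share of dropouts due to the cause plotted. All completers are followed to the end, so the cumulative incidence at the end equals the crude proportion, D × f. If other exits are censored at exit and the cause-specific hazards are proportional, 1-KM = 1 − (1 − D)^f.

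| D | f | Crude proportion D × f | 1-KM | Excess (points) |
|---|---|---|---|---|
| 27% | 1/3 | 9.0% | 10.0% | 0.96 |
| 27% | 1/2 | 13.5% | 14.6% | 1.06 |
| 27% | 2/3 | 18.0% | 18.9% | 0.93 |

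For the middle row, 1 − 0.73^0.5 = 1 − 0.8544 = 0.1456. In an arm of 184 the excess is 0.0106 × 184, about 2 subjects. Over the same three shares, the excess is 0.5 to 0.6 points at D = 20% and 1.6 to 1.9 points at D = 35%.

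If adverse events and subject withdrawal were the only two causes, split evenly, the two curves would end at 14.56% each. They would sum to 29.1%, against 27% on the all-cause curve.

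**Timing, at 27% split 13.5/13.5.**
- All adverse-event exits first: 1-KM = 13.5%, excess 0.
- All other exits first: 0.135/(1 − 0.135) = 15.6%, excess 2.1 points.
- 80% of adverse-event exits in the first 14 weeks and other exits uniform over 189 days, computed day by day: 14.2%, excess about 0.7 points.

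**The alternative convention.** If other-cause leavers stay in the risk set to the end of study, 1-KM = 13.5%, equal to the crude proportion, with no excess.

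**Between arms, adverse-event curve, assumed splits.**

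| Scenario | Arm | Dropout (AE + other) | 1-KM | Excess (points) |
|---|---|---|---|---|
| A | Tavapadon | 35% (20 + 15) | 21.82% | 1.82 |
| A | Placebo | 19% (5 + 14) | 5.39% | 0.39 |
| B | Tavapadon | 30% (28 + 2) | 28.32% | 0.32 |
| B | Placebo | 24% (12 + 12) | 12.82% | 0.82 |

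In A the true difference of 15.0 points is shown as 21.82 − 5.39 = 16.4. In B the true difference of 16.0 is shown as 28.32 − 12.82 = 15.5. Under proportional hazards the excess is roughly half the product of the two proportions. In B this gives 0.5 × 0.28 × 0.02 = 0.28 points for tavapadon and 0.5 × 0.12 × 0.12 = 0.72 points for placebo. It does not follow total dropout alone.

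**The case against.** The strongest reply is that the SAP never says other exits are censored. A reader might infer from the choice of Kaplan-Meier that it does, but the only written rule concerns completers. A program that keeps other-cause leavers at risk to the end of study would reproduce the crude proportion exactly. This stands: the documents show a missing rule, not a stated wrong one, and the overstatement depends on the usual convention being applied.

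A reader might also infer that the arm with more dropouts is always distorted more. The documents do not support this. They give no dropout by arm, and scenario B shows the order can reverse, because the excess depends on the number and timing of exits for other reasons.

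Finally, the crude figures are already planned: reasons for leaving the study (SAP 5.6), reasons for stopping the IMP (SAP 5.8), a summary of events leading to IMP discontinuation (SAP 5.15.1), and narratives for subjects who stop because of adverse events (Protocol 8.4.6.3). No test, threshold or decision is attached to the plots. This also stands, and it limits the importance of the point. It does not justify leaving a curve that may disagree with the table beside it when a matching method is available at no cost in data.

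**Conclusion.** The point holds as a minor one. For the two cause-specific curves the plan names a method without the rule needed to run it, and the default reading gives a curve that is never below, and normally above, the actual proportion. The size is about 1.1 points at the planned 27% dropout (14.6% against 13.5%), and 0 to 2.1 points depending on timing. The 1.1 rests on an assumed even split of causes and proportional hazards; the range rests on the even split only. Any between-arm effect is unknown in size and direction. The all-cause curve is unaffected, and neither the efficacy inference nor the planned tabulations of discontinuation change.

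**What to change.** In SAP 5.6, keep Kaplan-Meier for all-cause discontinuation. For discontinuation due to adverse events and due to subject withdrawal, plot Aalen-Johansen cumulative incidence by treatment group. State that every other discontinuation reason is a competing event and that completers are censored at end of study. Each curve will then end at the proportion in the table of reasons. The cost is one sentence in the SAP and one procedure option in the program. The reasons and dates of discontinuation are already needed for the planned plots.
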